7.4.1.7 Analysis for Japanese subjects

The same analysis as the primary analysis (Section 7.4.1.1) will be conducted for Japanese subjects.

7.4.2 Analysis of Secondary Endpoints

Refer to Section 10.2 Appendix 2. They includes categorical, continuous, and time-to-event variables, with "X" indicating that the variable will be analyzed. As for secondary variables, no multiplicity adjustment will be done. Basically, analysis of secondary endpoints will be performed by Initial Randomization Set and Treatment Sequence Set defined at Section 7.1.

The secondary variables and analyses are as follows:

<Initial Randomization Set>

- Categorical variables at each visit (including Baseline, Weeks 4, 8, 12, 12/ET) will be analyzed using logistic regression model, as described for the primary efficacy variable, unless otherwise specified in Section 10.2 Appendix 2.
- For continuous variables, raw value and change from baseline variables at each visit (Baseline, Weeks 4, 8, 12, 12/ET) will be analyzed using the ANCOVA model with treatment group (Placebo, ASP015K 100 mg, and ASP015K 150 mg) as the factor, and the prior biologic-DMARD-IR, concomitant DMARD at Baseline use, study region (Japan, Korea, and Taiwan), and baseline value as the covariates. In addition to this, sensitivity analysis to assess the impact of HAQ-DI caused by inappropriate description in the local questionnaire in Taiwan will be conducted similarly as described in 7.4.1.2.
- Time to the first response analysis will be analyzed similarly as described in 7.4.1.5.
 - ACR50-CRP
 - ACR70-CRP
 - DAS28-CRP <2.6
 - SDAI score <= 3.3
 - CDAI score <= 2.8
 - ACR/EULAR score for remissionAs for DAS28-CRP < 2.6, SDAI score <= 3.3, CDAI score <= 2.8, ACR/EULAR score for remission, if the event is occurred at baseline, then that subject is excluded from this analysis.
- Graphical analysis (including Baseline, Weeks 4, 8, 12, 12/ET).

- ACR20/50/70-CRP will be plotted for over time.
- The mean-standard deviation plot of actual values and changes from baseline will be presented for DAS28-CRP and DAS28-ESR.
- To visually explore possible relationships between ACR20-CRP and DAS28-CRP, 2-panel line graphs of DAS28-CRP over time will be plotted for ACR20-CRP responders (in 1 panel) and non-responders (in another panel). Similar graphs will be provided for DAS28-ESR.

<Treatment Sequence Set>

- Categorical variables at each visit (including Baseline, Weeks 4, 8, 12, 16, 20, 24, 28, 32, 36, 40, 44, 48, 52, EOT) will be summarized as described in Section 10.2 Appendix 2.
- For continuous variables, raw value and change from baseline variables at each visit (including Baseline, Weeks 4, 8, 12, 16, 20, 24, 28, 32, 36, 40, 44, 48, 52, EOT) will be summarized by descriptive statistics. Details are described in Section 10.2 Appendix 2.
- Graphical analysis (including Baseline, Weeks 4, 8, 12, 16, 20, 24, 28, 32, 36, 40, 44, 48, 52, EOT).
 - ACR20/50/70-CRP will be plotted for over time.
 - The mean-standard deviation plot of actual values and changes from baseline will be presented for DAS28-CRP and DAS28-ESR.

7.5 Analysis of Safety

In general, For AE Analysis up to Week 12 will be performed by Initial Randomization Set in SAF. AE Analysis from "Week 12 to Week 52 or Later" will be performed by Treatment Sequence Set in SAF. AE 100 Patient-Years analysis will be performed by Groups for Patient-Years. Details for analysis groups will be described in 10.3 Appendix 3.

For other safety analysis except for AE up to Week 12 will be performed by Initial Randomization Set in SAF. For other safety analysis except for AE up to Week 52 will be performed by Treatment Sequence Set in SAF. Details for analysis groups will be described in 10.4 Appendix 4.

7.5.1 Adverse Events

If an AE occurs on the same date as the initial dose date, the subject will be asked to select one of the following (see the eCRF page for AE): onset before initial dose of study drug or reference drug, onset after initial dose of study drug or reference drug. Any AEs occurring after initial dose of study drug or reference drug through the follow-up period will be considered treatment emergent.

Adverse events will be coded using the Medical Dictionary for Regulatory Activities (MedDRA).

All adverse events reported during the study period will be presented in subject listings.

Only TEAEs in the study period will be analyzed, and 2 types of analyses will be performed: TEAE occurrence analysis and TEAE per 100 patient-years analysis, as described below. TEAE occurrence analysis will be displayed by whole treatment period and by the following period. Primarily, TEAE occurrence analysis for Week 0 to Week 12 will be conducted in the view of comparison with placebo.

TEAE occurrence analysis for overall treatment period will be conducted in focus for ASP015K dose groups and reference group.

1. Week 0 to Week 12
2. Week 12 to Week 52 or Later

TEAE per 100 patient-years analysis will be displayed above category, and by overall period.

7.5.1.1 Adverse events

The coding dictionary for this study will be MedDRA 11.1. It will be used to summarize AEs by SOC and PT. Subjects reporting more than one AE for a given MedDRA PT will be counted only once for that term. Subjects reporting more than one AE within a SOC will be counted only once for the SOC total. Subjects reporting more than one AE will be counted only once in the overall AE total.

SOCs will be presented by descending frequency for 100 mg + 150 mg column, and PTs within SOC will be presented by decreasing frequency in the 100 mg + 150 mg.

Number and percentage of subjects with TEAE in the following AE categories will be summarized by SOC and PT for each treatment group, 100 mg + 150 mg, Total:

An overview table will include the following details:

- Number and percentage of subjects with TEAE
- Number and percentage of subjects with drug related TEAE
- Number and percentage of subjects with death
- Number and percentage of subjects with serious TEAE
- Number and percentage of subjects with drug related serious TEAE
- Number and percentage of subjects with Grade 3 or Higher in Severity TEAE
- Number and percentage of subjects with TEAE leading to permanent discontinuation of study drug or reference drug
- Number and percentage of subjects with drug related TEAE leading to permanent discontinuation of study drug or reference drug
- Number and percentage of subjects with serious TEAE leading to permanent discontinuation of study drug or reference drug

- Number and percentage of subjects with drug related serious TEAE leading to permanent discontinuation of study drug or reference drug

The number and percentage of subjects with TEAEs, as classified by SOC and PT will be summarized for each treatment group. Summaries will be provided for:

- TEAEs
- Drug related TEAEs, defined as any TEAE with possible, probable or missing relationship to study drug or reference drug as assessed by the investigator. Subjects reporting more than one TEAE for a given PT will be counted only once for that term in the most related category reported.
- Serious TEAEs
- Drug related serious TEAEs
- TEAEs by severity based on National Cancer Institute Common Terminology Criteria for Adverse Events (NCI-CTCAE) Grade (Grade 1 = mild, Grade 2 = moderate, Grade 3 = severe or medically significant, Grade 4 = life threatening, Grade 5 = death related to AE)
Subjects reporting more than one TEAE for a given PT will be counted only once for that term in the most severe category reported.
If a subject has an AE which has a missing severity, then the subject will be counted in the severity category of "Missing" (i.e., missing severity will not be imputed).
- Drug related TEAEs by severity
- Grade 3 or higher TEAEs by severity
- TEAEs by relationship to study drug or reference drug
Subjects reporting more than one TEAE for a given PT will be counted only once for that term in the most related category reported.
TEAE with missing relationship to study drug missing will be counted as drug related. Moreover, any TEAE with missing relationship to study drug or reference drug was counted as drug related (probable).
- TEAEs leading to death
- TEAEs leading to permanent discontinuation of study drug or reference drug
- Drug related TEAEs leading to permanent discontinuation of study drug or reference drug
- Serious TEAEs leading to permanent discontinuation of study drug or reference drug
- Drug related serious TEAEs leading to permanent discontinuation of study drug or reference drug
- TEAEs excluding serious adverse events that equal to or Exceed a threshold of 5% in Any Treatment Group
- Most common TEAEs (> 5% in any treatment group)
- Most common serious TEAEs (> 5% in any treatment group)
- The number and percentage of subjects with TEAEs by subgroups defined in Section 7.8
- The number and percentage of subjects with TEAEs of special interest.

Following adverse events of special interest are defined in the Appendix 8:

- Serious Infections
- Malignancies
- Herpes Zoster Related Disease (Herpes Zoster and Varicella)
- Herpes Zoster
- Varicella
- Infections That Require Intravenous Anti-infectious Therapy

In addition, the subgroup analysis of Sex, Age Group, Concomitant Steroid at Baseline, and Prednisone Dose at Baseline will be conducted.

7.5.1.2 Adverse Events Per 100 Patient-Years

In order to adjust for differences in subjects' durations in the study and the potential differential dropout rates between the treatment groups, TEAEs per 100 patient-years (PYs) will be calculated for each treatment group as follows:

Definition 1:

TEAEs per 100 PYs = $100 \times (\text{Number of subjects who had at least 1 incidence} / \text{Total PYs})$

Total PYs will be calculated by summing individual subjects' durations.

If subjects had at least 1 predefined AE, then the duration of these subjects are summed as from initial dose up to first incidence of predefined AEs.

If subjects had no predefined AE, then the duration of these subjects are summed as from initial dose through follow-up. Summed duration will be divided by 365.25 to represent per year.

Definition 2:

TEAEs per 100 PYs = $100 \times (\text{Number of TEAEs for all subjects in the treatment group} / \text{Total PYs in the treatment group})$.

For number of TEAEs for all subjects in the treatment group, multiple occurrences of the same TEAE in the same subject will be counted multiple times.

Total PYs will be calculated by summing subjects' durations in study through the follow-up period. Each subject's duration will be calculated as: $(\text{last date of follow-up in the study} - \text{date of initial dose of study drug} + 1) / 365.25$.

Patient-Year analysis will be calculated by Placebo, 100 mg, 150 mg, 100mg+150mg, ASP015K Total, Total.

The number of TEAEs and AEs per 100 PYs will be provided by Definition 2, for all TEAEs (if analyzable), by SOC and PT for each treatment group, ASP015K Total and Total.

Patient-Year analysis for following specified AE will also be conducted by Definition 1 with 95% confidence interval.

- Serious Infections
- Malignancies
- Herpes Zoster Related Disease (Herpes Zoster and Varicella)
- Herpes Zoster
- Varicella
- Infections That Require Intravenous Anti-infectious Therapy

Note: Definition will be provided in the Appendix 8.

Confidence Interval for TEAEs per 100 patient-years will be calculated for AE of special Interest based on following formula (assuming Poisson distribution).

- Upper limit of CI log (TEAEs per 100 PYs) : $exp\left(\log\left(\frac{A}{T}\right) + Z_{alpha} * \sqrt{\frac{1}{A}}\right)$
- Lower limit of CI log (TEAEs per 100 PYs) : $exp\left(\log\left(\frac{A}{T}\right) - Z_{alpha} * \sqrt{\frac{1}{A}}\right)$

A: Number of subjects who had at least 1 incidence

T: Total PYs by 100 PYs as one unit

$Z_{(alpha)}$: alpha % point of standard normal distribution

alpha = 0.025

In addition, the subgroup analysis of Sex, Age Group, Concomitant Steroid at Baseline, and Prednisone Dose at Baseline will be conducted.

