WHO-DD	World Health Organization Drug Dictionary
WPAI	Work Productivity and Activity Impairment Questionnaire

List of Key Terms

Terms	Definition of terms
Baseline	1) Values/findings observed prior to the initiation of study treatment, which are regarded as the starting point for comparison. 2) The time point at which those reference values/findings were observed.
Study period	The period of time from obtaining informed consent from the subject to the end of the final evaluation/observation specified in the protocol.
Investigational period	The period of time where major interests of protocol objectives are observed. In general, the subject will receive a test drug, comparative drug, or reference drug (possibly without randomization) during this period, which extends until the last post-treatment assessment is completed.
Follow-up period	The follow-up period will be 4 weeks (on a per-protocol basis) starting after the early-termination visit for withdrawn subjects and after the Week 52 visit for subjects who completed the study but are not willing to enroll into the extension study or those in the reference group who completed the study. For subjects who completed the study and wish to enroll into the extension study, the follow-up period will last for a maximum of 4 weeks starting after the Week 52 visit and ending at the initiation of the extension study treatment.
Subject	An individual who participates in a clinical study as a recipient of either the test drug(s) or reference drug(s), or as a control.
Week 12/ET	Week 12 or early termination before Week 12
EOT	Week 52 or early termination before Week 52
Study discontinuation	The act of concluding participation, prior to completion of all protocol-required elements, in a study by an enrolled subject. Four categories of discontinuation are distinguished: a) dropout: Active discontinuation by a subject (also a noun referring to such a discontinued subject); b) discontinuation initiated by the investigator or other responsible personnel (e.g., for cause); c) loss to follow-up: discontinuation of participation without notice or action by the subject; d) sponsor-initiated discontinuation. Note that subject discontinuation does not necessarily imply exclusion of subject data from analysis.
Variable	A characteristic under study that varies: any attribute, phenomenon, or event that can have different qualitative or quantitative values.

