Blood sampling for post-dose drug concentration ⁴⁾				○																
Blood sampling for PD (biomarkers)			○	○	○	○				○						○	○	○	○	▲
Blood sampling for PD (lymphocyte subset)			○	○	○	○				○						○	○	○	○	▲
Informed consent for PGx research (relevant sites only) ⁴⁾			○																	
Blood sampling for PGx (relevant sites only) ⁴⁾			○																	

Visit	Initiation of Screening ¹⁾	Screening Test Period	0 W	4 W	8 W	12 W	16 W	20 W	24 W	28 W	32 W	36 W	40 W	44 W	48 W	52 W	Early Termination	Follow-up ²⁾	Unscheduled Visit
Visit day	-1 at latest	-28 to -1	1	29	57	85	113	141	169	197	225	253	281	309	337	365	Within 2 days of withdrawal	28 days after Week 52 or early termination visit	-
Allowable range from specified date				±7	±7	±7	±7	±7	±7	±7	±7	±7	±7	±7	±7	±7	+2	±7	-
Study drug/reference drug																			
Confirmation of remaining unused drugs				○	○	○	○	○	○	○	○	○	○	○	○	○	○		
Prescription			○	○	○	○	○	○	○	○	○	○	○	○	○				

The symbol "○" designates mandatory items, whereas the symbol "▲" denotes the optional items to be investigated on the basis of the clinical judgment of the investigator/sub-investigator.

For details, see the respective Sections of the protocol.

- 1) Subjects who have signed the informed consent will undergo evaluation of DMARD response at the screening visit.
- 2) Follow-up will not be performed for subjects starting the extension study immediately after the Week 52 visit.
- 3) For details of the test parameters, refer to protocol Section 5.4.4.
- 4) Subjects in the reference group will not undergo these procedures.
- 5) For pregnancy tests, serum samples will be used at the screening visit, and urine samples will be used at and after the baseline visit.
- 6) Central ECG should be performed on the same day as blood sampling for post-dose drug concentration at Week 4 or Week 8 before and after study drug administration.

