6.2 Safety Variables

- AEs
- Vital signs (body temperature, pulse rate and blood pressure in sitting position)
- Body weight
- 12-lead ECG
- Central ECG
- Chest radiography
- Laboratory assessments

Treatment emergent adverse events (TEAEs) will be defined as any adverse event that started or worsened in severity after initial dose of study drug or reference drug through Week52 or Withdrawal.

AE for the subjects who switched ASP015K 100 mg or ASP150 mg from Placebo at Week 12 will be handled as follows:

- AE onset before the first dose of week12 study drug will be considered to be occurred at Placebo.
- AE onset after the first dose of week12 study drug will be considered to be occurred at ASP015K 100 mg or 150 mg, which is switched treatment from Placebo.

A drug-related TEAE is defined as any TEAE with possible, probable or missing relationship to study drug or reference drug as assessed by the investigator.

Moreover, any TEAE with missing relationship to study drug or reference drug was counted as drug related (probable).

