Drug related serious TEAEs leading to permanent discontinuation of study drug or reference drug		X1	
TEAEs excluding serious adverse events that equal to or Exceed a threshold of 5% in Any Treatment Group	X2		
Most common TEAEs (> 5% in any treatment group)	X3	X1	X2
Most common serious TEAEs (> 5% in any treatment group)	X3	X1	X2
TEAEs by subgroups defined in Section 7.8.		X1	
The number and percentage of subjects with TEAEs of special interest	X3	X1	
Serious Infections	X3 ^{#1}	X1 ^{#1}	
Malignancies	X3 ^{#1}	X1 ^{#1}	
Herpes Zoster Related Disease (Herpes Zoster and Varicella)	X3 ^{#1}	X1 ^{#1}	
Herpes Zoster	X3	X1	
Varicella	X3	X1	
Infections That Require Intravenous Anti-infectious Therapy	X3	X1	
Subgroup of TEAEs		X1	
Sex		X1	
Age Group		X1	
Prior Anti-TNF DMARD Use		X1	
Prior Biologic DMARD-IR		X1	
Concomitant DMARD Use at Baseline		X1	
Study Region		X1	
Duration of RA		X1	

Number of Prior DMARDs Used		X1	
Number of Prior Biologic DMARDs Used		X1	
MTX Dose at Baseline		X1	
Concomitant DMARD Category at Baseline		X1	
Protocol Version Number		X1	
Concomitant Steroid at Baseline		X1	
Prednisone Dose at Baseline		X1	
Subgroup of TEAEs of special interest		X1	
Sex		X1	
Age Group		X1	
Concomitant Steroid at Baseline		X1	
Prednisone Dose at Baseline		X1	

X1: Placebo, 100mg, 150mg, Reference

X2: 100mg, 150mg, Placebo to 100 mg at Week 12, Placebo to 150 mg at Week12, Reference

X3: 100mg, 150mg, Reference

#1: Subgroup analysis based on study region or protocol version number will be also presented.

#2: Subgroup analysis based on study region will be also presented.

Table 22. Patient-year analysis

	Week 0 to Week 12	Overall Period
TEAEs (provided by “Definition 2” in 7.5.1.2)	X1	X3
TEAEs of special interest (provided by “Definition 1” in 7.5.1.2)	X1	X3
Serious Infections	X1	X3
Malignancies	X1	X3
Herpes Zoster Related Disease (Herpes Zoster and Varicella)	X1	X3
Herpes Zoster	X1	X3
Varicella	X1	X3
Infections That Require Intravenous Anti-infectious Therapy	X1	X3
Subgroup		X3
Sex		X3
Age Group		X3
Concomitant Steroid at Baseline		X3
Prednisone Dose at Baseline		X3

X1: Placebo, 100mg, 150mg, Reference

X3: 100mg, 150mg, Reference

10.4 Appendix 4: Overview of Clinical Laboratory Evaluation, Vital Signs, and Electrocardiograms (ECGs) analyses

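### SAP 7.5.1.2 gives person-time no Week 12 stop, yet Table 22 uses it for a Week 0 to 12 column that includes placebo

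*SAP*

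**What the plan says.** SAP 7.5.1.2 gives two definitions of a rate per 100 patient-years, with the stated aim of adjusting for differing time in study and possible differential dropout.

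- Definition 1 (events of special interest) counts a subject with an event up to the first event. For the rest: "If subjects had no predefined AE, then the duration of these subjects are summed as from initial dose through follow-up".
- Definition 2 (all TEAEs) sums "durations in study through the follow-up period" for every subject: last follow-up date minus first dose date, plus 1, divided by 365.25.

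SAP Appendix 3, "Table 22. Patient-year analysis", names both definitions and gives each a Week 0 to Week 12 column (placebo, 100 mg, 150 mg, Reference) and an overall column (100 mg, 150 mg, Reference). SAP 7.5.1 also asks for patient-year results by period.

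For subjects who start on placebo, SAP 6.2 splits events at the switch: "AE onset before the first dose of week12 study drug will be considered to be occurred at Placebo", and "AE onset after the first dose of week12 study drug will be considered to be occurred at ASP015K 100 mg or 150 mg". No section splits their time at that point.

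The end of follow-up varies. The footnote to SAP Table 1 says "Follow-up will not be performed for subjects starting the extension study immediately after the Week 52 visit". For other completers wishing to enter the extension, the SAP key terms say "the follow-up period will last for a maximum of 4 weeks starting after the Week 52 visit". Everyone else has a visit 28 days after Week 52 or after early termination.

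**The concern.** An incidence rate needs events and time at risk from the same interval. As written, the placebo events in the Week 0 to 12 column come from about 12 weeks, while the formula supplies time from the whole study. Most of that time is spent on ASP015K after the switch.

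Table 22's overall column has no placebo group. The Week 0 to 12 column therefore holds that table's only placebo rates for serious infection, malignancy and herpes zoster. A reader would naturally set them beside the overall ASP015K and etanercept rates. If the time is not cut, the placebo figures are too low for that use.

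**Working it through.** The SAP states no patient-year total or rate, so there is no planned figure to reproduce.

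**Inputs** (SAP Table 1 and the visit windows in 7.11). Week 12 is Day 7 × 12 + 1 = 85, with a window to Day 92. Week 52 is Day 7 × 52 + 1 = 365. Follow-up is Day 365 + 28 = 393. Nominal placebo time is Days 1 to 84, or 84 days.

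**Placebo completer, events cut at Week 12, time as written**

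| Switch day | Direct extension entry | 28-day follow-up |
|---|---|---|
| Day 85 | 365/84 = 4.35 | 393/84 = 4.68 |
| Day 92 | 365/91 = 4.01 | 393/91 = 4.32 |

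Of the 365 to 393 counted days, 365 − 84 = 281 run from the switch to Week 52: 281/365 = 77%, or 281/393 = 72%.

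**Illustration, Definition 2** (assumed: 100 placebo completers and 100 TEAEs in Weeks 0 to 12). With a Week 12 stop, 8,400/365.25 = 23.0 patient-years, or 434.8 per 100. As written, the rate is 100.1 (365 days each) or 92.9 (393 days each).

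**Definition 1 with events** (assumed: 100 completers, mean event day 42). With 1 event: (99 × 365 + 42)/(99 × 84 + 42) = 4.33, or 4.66 using 393 days. With 10 events: 4.17 to 4.49.

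**Whole arm with dropout** (assumed uniform over Days 1 to 364; mean day 182.5)

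- 10% dropout, Day 85 switch, 28-day follow-up for all. Written time is 0.9 × 393 + 0.1 × (182.5 + 28) = 374.8 days. Correct time, capped at Day 84, is 83.0. Ratio 4.51.
- 40% dropout, Day 85 switch, no follow-up after withdrawal, direct entry. Written time is 0.6 × 365 + 0.4 × 182.5 = 292.0. Correct time is 80.2. Ratio 3.64.
- The same with a Day 92 switch: 292.0/86.5 = 3.38.

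**Ratios within the column, if all arms are diluted.** The ASP015K/placebo rate ratio is multiplied by the placebo dilution divided by the ASP015K dilution. Assume early dropout of 20% (placebo) and 5% (ASP015K) at mean day 42.5, late dropout at mean day 224.5, direct entry, and no follow-up after withdrawal. Correct times are then 75.7 and 81.9 days.

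| Late dropout, placebo-origin vs ASP015K | Placebo dilution | ASP015K dilution | Multiplier |
|---|---|---|---|
| 0% vs 0% | 300.5/75.7 = 3.97 | 348.9/81.9 = 4.26 | 0.93 |
| 10% vs 30% | 286.5/75.7 = 3.78 | 306.7/81.9 = 3.74 | 1.01 |
| 30% vs 10% | 258.4/75.7 = 3.41 | 334.8/81.9 = 4.09 | 0.84 |

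So the shift is modest beside the fourfold dilution, and late dropout can change its direction.

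**Related wording**

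- SAP 7.5.1.2 lists an ASP015K Total group without saying who is in it, and omits Reference. Table 22 has Reference but no ASP015K Total. If that total includes the switchers, the formula adds 84 placebo days to each completing switcher: 84/281 = 30% (direct entry) or 84/309 = 27% (28-day follow-up).
- SAP 7.5.1 calls for a patient-year display from Week 12 onward; Table 22 has none.
- TEAEs end at Week 52 or withdrawal in SAP 6.2 but at the end of follow-up in 7.5.1. If the former holds, a completer with a 28-day follow-up has 28/365 = 7.7% too much time, and a direct entrant none.

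**The case against.** The best defence is that a Week 12 limit applies to both parts of the rate. SAP 7.5 says "AE Analysis up to Week 12 will be performed by Initial Randomization Set in SAF", and Table 3 gives that set a Week 0 to Week 12 scope. SAP 7.5.1 sets the reporting periods in body text, and 7.3.1 tabulates exposure up to Week 12. A careful programmer would probably cut the time as well. This stands as evidence of intent, and the dilution arises only if events are cut and time is not.

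It does not remove the gap. SAP 7.5.1.2 is an explicit formula with a named end date, and Table 22 points to it by name. Where the authors wanted a Week 12 stop they wrote one: 7.4.1.6 censors the day before Week 12 dosing, and the 7.11.6 windows stop before the first Week 12 dose. The intended cut is also not unique. It could be Day 84, the actual day before dosing, or Day 92, and etanercept has no switch to define it.

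It is also fair that the consequence is limited. Table 21 gives the events of special interest by occurrence for Week 0 to 12 with placebo, and 7.5.1 makes occurrence the primary placebo comparison. With about 23 placebo patient-years, rates of rare events will be imprecise however time is counted.

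A reader might infer that the placebo comparison of safety is wrong by a factor of four. The documents do not support that, because the other arms in the column use the same formula. Nor do they support saying that the patient-year groups are left wholly undefined: SAP 7.5 refers the analysis groups to Appendix 3, and Table 22 lists them. What remains is a mismatch with the list in 7.5.1.2.

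**Conclusion.** The rule is wrong as written, although the context points to an intended Week 12 cut. With events limited to Week 12 and time taken from the formula, the placebo rate is 4.35- to 4.68-fold too low for a completer on the nominal schedule and 4.01- to 4.32-fold with a Day 92 switch. For the whole arm it is about 3.4- to 4.5-fold under assumed dropout of 10% to 40%. The completer factors rest on the visit calendar; the whole-arm range rests on dropout patterns that the documents do not give, so it is not a bound.

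The error is confined to the absolute Week 0 to 12 patient-year rates and to setting them beside the overall-period rates. Ratios within the column move only with differential dropout, in a direction that depends on late dropout. The occurrence tables are unaffected. This should be fixed, but it does not threaten the trial's main safety comparison.

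**What to change.** In SAP 7.5.1.2, state that Week 0 to 12 person-time ends at the earliest of:

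- the first event (Definition 1 only);
- the day before the first Week 12 dose of study drug (for Reference, the day before the Week 12 visit, at latest Day 92);
- the TEAE end date.

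Then:

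- Say who is in ASP015K Total. If it includes subjects switched from placebo, count their time from the first ASP015K dose.
- Reconcile the group list in 7.5.1.2 and the periods in 7.5.1 with Table 22.
- Use one TEAE end date in 6.2, 7.5.1 and the denominator.

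The cost is SAP wording and programming. No new data are needed.
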